11.3 Overall Survival (Groups 1, 2, and 3a)

Overall Survival (OS) is defined as the time between the date of first dose of study drug to the date of death from any cause and will be calculated as:

$$\text{Date of Death or Censoring} - \text{Date of First Study Drug Dose} + 1$$

Patients who were lost to follow-up or did not die on study will be censored on the last known date to be alive and will be calculated as:

$$\begin{aligned} \text{Date of last response assessment or end-of-study visit or follow-up visit (whichever is latest)} \\ - \text{Date of first study drug dose} + 1 \end{aligned}$$

Kaplan-Meier methods will be used for the analysis of overall survival. Median (with corresponding 2-sided 95% CI), quartiles (25th and 75th percentiles), minimum, and maximum duration of response time will be displayed by Phase 2a dose expansion group. A Kaplan- Meier figure of OS will be provided as standard for time-to-event endpoints.

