6.3. ENROLLMENT

Patients are considered enrolled:

- Within 28 days of beginning screening
- After the results for all screening procedures have been received by the study site
and
 - After the patient has met all inclusion and exclusion criteria and therefore is deemed eligible for the study by the Principal Investigator or designee
and
 - After Sponsor approval is received and documented by signature per the agreed upon process
 - The enrollment date is the date of the Sponsor's signature

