8.2. ANALYSIS POPULATION

The following populations are defined for statistical purposes:

Population	Description
Enrolled	All patients who sign consent
Treated/Full Analysis Set	All patients who receive at least 1 dose of SQL70 biopolymer and 1 dose of SQP33 protodrug
Efficacy Evaluable	All patients who receive at least 1 dose of SQL70 biopolymer and 1 dose of SQP33 protodrug and undergo at least 1 post baseline tumor evaluation
Safety	All patients who received at least 1 dose of SQL70 biopolymer and/or SQP33 protodrug
PK	All patients in the Safety Population who have the necessary Day 1 and on-study measurements to provide interpretable results for the specific parameters of interest
Biomarker	All patients with available biomarker data

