- PFS is defined as the time between the date of enrollment and the date of the initial objectively documented tumor progression per RECIST v1.1 or date of death from any cause, whichever occurs first.
- Time from enrollment to first subsequent therapy (TFST) is defined as the time between the date of enrollment to the date of first new anti-cancer therapy.
- OS is defined as the time between the date of enrollment to the date of death from any cause.

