3.5 Efficacy Endpoints

- Objective response rate (ORR) per Response Evaluation Criteria in Solid Tumors (RECIST) v1.1.
- Overall Survival (OS)
- Time from enrollment to first subsequent therapy (TFST)
- Plasma concentration and PK parameters for SQP33 protodrug and active Dox following SQ3370 treatment.
- Group 1: Advanced High-risk Soft Tissue Sarcoma of the Extremity
 - Histopathological Response
 - Surgical outcome amputation/limb-salvage vs planned
 - Disease-free survival
 - Local recurrence-free survival [Time Frame: 2 years]
 - Distant recurrence-free survival
 - Symptomatic disease control
- Group 2: Comparison of the RP2D of SQ33 total dose in mg/m² administered every 21 days administered over 3 vs over 5 days
 - Compare safety and tolerability of two infusion schedules of SQP33 (3-day vs 5- day)
 - Pharmacokinetic comparison of the two infusion schedules
 - PFS per RECIST v1.1
 - DoR per RECIST v1.1
 - DCR per RECIST v1.1
- Group 3a: Head & Neck
 - DoR per RECIST v1.1
 - PFS per RECIST v1.1
 - Time to local-regional progression or distant progression per RECIST v1.1
 - Local-regional control per RECIST v1.1
 - DCR per RECIST v1.1

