11.5 Progression Free Survival (Groups 2 and 3a)

Progression Free Survival (PFS) is defined as the date of first dose of study drug to the date of the initial objectively documented tumor progression per RECIST v1.1 or date of death from any cause whichever occurs first and will be calculated as:

$$\begin{aligned} \text{Date of Disease Progression or Death Date (whichever is earliest)} - \text{Date of First Study} \\ \text{Drug} + 1 \end{aligned}$$

Patients who were lost to follow-up or had not progressed/died on study will be censored on the date of their last disease assessment or end-of-study visit or subsequent therapy (whichever is earliest) and will be calculated as:

Date of last response assessment or end-of-study visit or subsequent therapy (whichever is earliest) – Date of first study drug dose + 1

NOTE: If a patient does not have post-baseline tumor assessment or clinically determined progression and have not died, then the PFS will be censored at Day 1;

Kaplan-Meier methods will be used for the analysis of duration of stable disease. Median (with corresponding 2-sided 95% CI), quartiles (25th and 75th percentiles), minimum, and maximum duration of response time will be displayed. A Kaplan-Meier figure will be provided as standard for time-to-event endpoints.

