11.6 Time to First Subsequent Therapy (Groups 1, 2 and 3a)

Time to first subsequent therapy (TFST) is defined as the time between the date of first dose of study drug to the date of first new anti-cancer therapy (subsequent therapy). .

At this time, there is not enough information regarding this endpoint. The data collection and planned analysis of this endpoint will be discussed in the next version of this SAP after the safety run-in and/or Simon Stage 1 analysis. However, Kaplan-Meier methods will be utilized for data analysis of this endpoint.

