11.10 Local Recurrence-Free Survival, Time Frame: 2 Years (Group 1)

Local-recurrence-free survival is defined as time between the date of enrollment and the date of local recurrence/relapse or death from any cause, whichever occurs first.

At this time, there is not enough information regarding this endpoint. The data collection and planned analysis of this endpoint will be discussed in the next version of this SAP after the safety run-in and/or Simon Stage 1 analysis. However, Kaplan-Meier methods will be utilized for data analysis of this endpoint.

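### The Phase 2a SAP starts four time-to-event endpoints at first dose and three at enrolment, so linked endpoints disagree for the same event; the protocol starts all seven at enrolment

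*SAP*

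**What the plan says.** Protocol 8.4.2.2 measures seven time-to-event endpoints from enrolment: OS, PFS, time to first subsequent therapy (TFST), disease-free survival (DFS), local recurrence-free survival (LRFS), distant recurrence-free survival (DRFS) and time to local-regional or distant progression. For OS it reads "OS is defined as the time between the date of enrollment to the date of death from any cause".

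The Phase 2a SAP splits them.

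- **From first dose:** OS in 11.3 ("Overall Survival (OS) is defined as the time between the date of first dose of study drug"), PFS in 11.5 ("Progression Free Survival (PFS) is defined as the date of first dose of study drug"), TFST in 11.6 ("Time to first subsequent therapy (TFST) is defined as the time between the date of first dose of study drug") and DFS in 11.9.
- **From enrolment:** LRFS in 11.10 ("Local-recurrence-free survival is defined as time between the date of enrollment and the date of local recurrence/relapse or death from any cause"), DRFS in 11.11 and time to local-regional or distant progression in 11.13.

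SAP section 16, the table of changes from the protocol, contains only N/A. The SAP's endpoint list in 3.5 still uses the name "Time from enrollment to first subsequent therapy (TFST", which contradicts 11.6.

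On the enrolment date, Protocol 6.3 states "The enrollment date is the date of the Sponsor's signature", to be given after screening results, eligibility and sponsor approval. Protocol 8.2 uses the label Enrolled for a population, "All patients who sign consent". SAP section 6 repeats that definition, and SAP 10.1 counts screen failures as enrolled.

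SAP section 9 assigns time-to-event endpoints to the Full Analysis Set, which contains only patients who received both components of study treatment.

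**The concern.** Endpoints that share events should share a clock. In Group 1, if every recurrence is classed as local or distant, DFS ought to equal the earlier of LRFS and DRFS. With different origins it is shorter than either for the same event. In Group 3a, one documented progression yields a PFS that is shorter than the time to progression.

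The enrolment clocks also sit awkwardly with the analysis set. A patient must be alive at first dose to be in it, so the interval from enrolment to first dose cannot contain a death. That interval lengthens the LRFS and DRFS clocks, which count deaths, and no time on it is at risk of death.

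Finally, four origins have moved away from the protocol without being listed as a change, in a SAP that says it supersedes the protocol's statistical considerations. A reader of the study report would not know that the clocks differ.

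**Working it through.** The plan states no figure that depends on the time origin, so there is nothing to reproduce. The check is a comparison of text, followed by date arithmetic.

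**Step 1: origins side by side**

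| Endpoint | Protocol 8.4.2.2 | Phase 2a SAP |
|---|---|---|
| OS | enrolment | first dose (11.3) |
| PFS | enrolment | first dose (11.5) |
| TFST | enrolment | first dose (11.6); enrolment in the name in 3.5 |
| DFS | enrolment | first dose (11.9) |
| LRFS | enrolment | enrolment (11.10) |
| DRFS | enrolment | enrolment (11.11) |
| Time to local-regional or distant progression | enrolment | enrolment (11.13) |

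**Step 2: possible size of the gap.** Let g be the days from enrolment to first dose. Under Protocol 6.2, screening starts on the day of consent (Day -28 at the earliest), there is no Day 0, and the patient must be enrolled by Day 1. Consent can therefore precede first dose by up to 28 days. The sponsor's signature under 6.3 can fall from screening up to Day 1, so g lies between 0 and 28 days and may be near zero. The documents give no typical value; 7, 14 and 28 below are assumptions.

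**Step 3: one event, two clocks.** Take a local recurrence 200 days after first dose. The SAP's add-one-day convention for OS and PFS is applied to both endpoints here, as an assumption.

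- DFS = 200 + 1 = 201 days.
- LRFS = 200 + g + 1 = 201, 208, 215 or 229 days for g = 0, 7, 14 or 28.

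The difference is exactly g. The same holds for PFS against time to progression in Group 3a.

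**Step 4: scale for LRFS.** The two-year frame is 2 × 365.25 = 730.5 days, using the SAP 8.6 conversion.

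- 7/730.5 = 1.0%
- 14/730.5 = 1.9%
- 28/730.5 = 3.8%

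**Step 5: effect on a two-year estimate.** Assume an exponential distribution from first dose, no events before it and the same g for every patient. If the two-year proportion from first dose is S, the rate is λ = −ln(S)/730.5, and the proportion at two years from enrolment is exp(−λ(730.5 − g)).

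| S from first dose (assumed) | g = 7 | g = 14 | g = 28 |
|---|---|---|---|
| 25% | 25.3% | 25.7% | 26.4% |
| 50% | 50.3% | 50.7% | 51.3% |

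The shift is about 0.3 to 1.4 percentage points.

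**Step 6: what does not move.** The Simon boundaries for Groups 1 and 3a and the Group 2 continuation rule rest on response counts and toxicity. None uses any of these clocks.

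**The case against.** The strongest reply is that the SAP is unfinished on this point. Sections 11.6, 11.9, 11.10, 11.11 and 11.13 each say that too little is known about the endpoint and leave data collection and analysis to the next version. The running header shows version 0.1 with an incomplete date. Only OS and PFS have worked formulas. The Group 1 conflict is therefore between three deferred endpoints. This is fair, and it makes the point a drafting item. It does not explain the mixture, because DFS and TFST carry the same deferral and were moved to first dose all the same.

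A reader might also infer that the enrolment date is defined in two ways. The documents do not support that. Only Protocol 6.3 defines a date. Protocol 8.2 and SAP section 6 define a population that shares the label, and Protocol 6.1 calls patients who have signed consent screened. What stands is looser: SAP 10.1 uses the consent-based sense, and the SAP gives no enrolment date of its own, so a programmer working from it alone could pick the wrong one.

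Third, first dose is not the only possible remedy. Returning the four endpoints to enrolment, dated by Protocol 6.3, would also restore consistency and would follow the protocol. That is correct, and the choice of first dose has to be argued for.

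**Conclusion.** The inconsistency is real and minor. Four of seven endpoints were moved to first dose, three were not, and the move is undeclared. For the same event, linked endpoints differ by the gap from enrolment to first dose. That gap is not given in the documents, is at most 28 days, and may be near zero under the sponsor-signature date. Against the two-year LRFS frame the maximum is 3.8%. The estimate in percentage points rests on the exponential illustration and a common gap.

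A reader might set 28 days against the 11-week median time to progression in Protocol 1.1.2 and report 28/77 = 36%. The plan does not support that as the size of the problem. It requires enrolment to mean consent, against Protocol 6.3, and every patient to use the whole screening window. Its denominator is a historical subgroup median under a combination regimen that the plan uses as a comparator for none of these endpoints.

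Nor does the mismatch threaten the trial's decisions. These are secondary endpoints summarised by Kaplan-Meier methods without a hypothesis test, and no sample size, error rate or Simon rule depends on them.

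**What to change.** In the SAP version already promised, use one origin for all seven endpoints. First dose is the better choice: it matches the dosed-only analysis set and the four endpoints already moved, and it removes the interval in which death cannot occur. In practice:

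- Change 11.10, 11.11 and 11.13 to first dose.
- Record the change of origin for all seven endpoints in section 16.
- Rename TFST in section 3.5 to agree with 11.6.
- Wherever an enrolment date is kept, tie it to Protocol 6.3 and not to the consent-based Enrolled population.

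The window for best overall response in 11.1 and 11.4 also opens at enrolment, while SAP 8.6 counts responses after treatment starts. Aligning it is optional tidying, because Protocol 6.18 times on-treatment scans every 6 weeks from Cycle 1 Day 1.

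The cost is SAP wording, with no new data. The one small downside is a wider departure from the protocol's enrolment origin, which is why the section 16 entry is needed.

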11.4 Disease Control Rate (Group 2 and 3a)

Disease control rate (DCR) is defined as the proportion of patients whose BOR is CR or PR or SD ≥ 60 -days, BOR is defined as the best response designation, recorded between the date of enrollment and the date of the initial objectively documented tumor progression per RECIST v1.1, date of death from any cause, or the date of subsequent therapy, whichever occurs first. For participants without documented progression or subsequent therapy, all available response designations will contribute to the BOR determination.

The disease control rate (DCR) will be summarized with the number and percentage of patients along with the corresponding two- sided 95% exact confidence interval (CI).by Phase 2a expansion group.

11.5 Progression Free Survival (Groups 2 and 3a)

Progression Free Survival (PFS) is defined as the date of first dose of study drug to the date of the initial objectively documented tumor progression per RECIST v1.1 or date of death from any cause whichever occurs first and will be calculated as:

$$\begin{aligned} \text{Date of Disease Progression or Death Date (whichever is earliest)} - \text{Date of First Study} \\ \text{Drug} + 1 \end{aligned}$$

Patients who were lost to follow-up or had not progressed/died on study will be censored on the date of their last disease assessment or end-of-study visit or subsequent therapy (whichever is earliest) and will be calculated as:

Date of last response assessment or end-of-study visit or subsequent therapy (whichever is earliest) – Date of first study drug dose + 1

NOTE: If a patient does not have post-baseline tumor assessment or clinically determined progression and have not died, then the PFS will be censored at Day 1;

Kaplan-Meier methods will be used for the analysis of duration of stable disease. Median (with corresponding 2-sided 95% CI), quartiles (25th and 75th percentiles), minimum, and maximum duration of response time will be displayed. A Kaplan-Meier figure will be provided as standard for time-to-event endpoints.

11.6 Time to First Subsequent Therapy (Groups 1, 2 and 3a)

Time to first subsequent therapy (TFST) is defined as the time between the date of first dose of study drug to the date of first new anti-cancer therapy (subsequent therapy). .

At this time, there is not enough information regarding this endpoint. The data collection and planned analysis of this endpoint will be discussed in the next version of this SAP after the safety run-in and/or Simon Stage 1 analysis. However, Kaplan-Meier methods will be utilized for data analysis of this endpoint.

11.7 Histopathologic Response (Group 1)

Patients will see their surgeon and medical oncologist after Cycle 4 to determine if the tumor(s) has shrunk enough for salvage surgery instead of amputation. The surgeon and medical oncologist may elect that the patient continue on therapy and have another consultation after additional cycles.

When the surgery does take place, a tumor section will be analyzed to determine if there is a pathological complete response or pathological partial response.

The histopathologic response categories (CR+PR) will be summarized with the number and percentage of patients along with the corresponding two- sided 95% exact confidence interval (CI).by Phase 2a expansion groups.

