 - Patients will enroll at the RP2D of SQ3370. It is anticipated that the size of tumors given the stage and inclusion criteria eligible for enrollment will be potentially larger than in Phase 1, this group will receive a fixed dose of SQL70 (20 mL). All patients are planned to receive 2 cycles of SQ3370 and undergo a disease reevaluation per RECIST 1.1. All patients without evidence of disease progression after initial 2 cycles, will then undergo an additional 2 cycles of treatment and have a presurgical disease re-evaluation and proceed to definitive surgical procedure(s). (See [APPENDIX H – Schedule of Assessments – Expansion Group 1: Extremity STS](#) for details).
 - Only patients who have had objective evidence of response or whom in the opinion of the multidisciplinary treatment team determined to have achieved a clinical benefit may defer surgery at this point. Note that the study will allow up to 4 additional cycles, at which point all patients should undergo exploratory surgery and or tumor resection.
 - If a patient with Stage III had a radiological and surgical complete response (CR) they may receive up to 4 additional cycles, but no patient may exceed 12 cycles within the study. Stage IV patients may continue post op chemotherapy. Any patient group III or IV must have accessible lesions or the primary tumor that is deemed adequate for post operative intratumoral injection. If a patient receives post-operative radiation which is allowed on study, they meet End of Treatment criteria and will not receive further SQP3370 (see section [3.1.5 End of Treatment](#)).
 - Any patient at any point who has been determined to have progressive disease has reached end treatment and will proceed to a definitive surgical treatment, note pre-operative radiation is allowed for patients with progressive disease pre-operatively on study at this point.
 - Subjects will be treated with the RP2D of SQ3370 every 21 days (1 cycle) up to 12 cycles or until other treatment discontinuation criteria are met (see section [3.1.5 End of Treatment](#)). On Day 1 of each cycle, the subject will receive an injection of SQL70 biopolymer into the tumor (20 mL), followed by 5 days of SQP33 infusion starting 3 hours ± 30 min after the SQL70 biopolymer injection.

- Group 2: Unresectable STS locally advanced or metastatic.

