Only patients who have had objective evidence of response, or whom in the opinion of the multidisciplinary treatment team, have achieved a clinical benefit may defer surgery at this point, and the study will allow up to 4 additional pre-op cycles, at which point patients should undergo exploratory surgery and or tumor resection. It is recommended that the surgical team place markers at the tumor margins to direct SQL70 dosing post resection. Post operatively subject with good responses may receive up to 4 additional cycles but not to exceed 12 cycles within the study. Surgical markers will be used to indicate the tumor bed for injection with SQL70.

Any patient at any point who has been determined to have progressive disease has reached the end of treatment and will proceed to a definitive surgical treatment. Note: pre-operative radiation

is allowed for patients with PD pre-operatively on study at this point. It is encouraged to keep subjects on study and to evaluate surgical specimens as per planned biomarker and pathological assessments. See [Schedules of Assessments Appendix H](#).

Group 2: Unresectable Soft Tissue Sarcoma with a Comparison of the RP2D of SQP33 administered over 3 vs 5 days

Patients will enroll at the RP2D of SQP33 given over 3 or 5 days and will receive a fixed dose of SQL70 (10 mL) on Day 1 of each cycle.

To compare safety and tolerability of the RP2D in two infusion schedules of SQP33 (3-day vs 5-day) in locally advanced, unresectable, each treatment group will maintain the total dose of SQP33 per cycle and compare two different infusion schedules while receiving the same dose and timing of SQL70. All subjects will commence treatment with SQP33 within 3 hours ± 30 minutes.

Table 2: Group 2 SQP33 Protodrug RP2D (% Administered) Per Day

	Day 1	Day 2	Day 3	Day 4	Day 5
5-Day Administration	20%	20%	20%	20%	20%
3-Day Administration	20%	40%	40%	NO Treatment	NO Treatment

See Pharmacy Manual for additional details.

Any patient at any point who has been determined to have progressive disease has reached the end of treatment, any subject completing 12 cycles of treatment will also have been deemed to have reached the end of treatment. See [Schedules of Assessments Appendix I](#) and [Appendix J](#).

Group 3a: Head and Neck

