Only patients who have had objective evidence of response or whom in the opinion of the multidisciplinary treatment team determined to have achieved a clinical benefit may defer surgery at this point, the study will allow up to 4 additional cycles pre-operatively, at which point all patients should undergo exploratory surgery and or extremity tumor resection.

If a patient had a response, they may receive up to 4 additional cycles post operatively but not to exceed 12 cycles within the study. Surgical markers will be used to indicate the tumor bed for injection with SQL3370 or if suitable for the metastatic patients, a metastatic lesion may be injected.

Any patient at any point who has been determined to have progressive disease has reached the end of treatment and will proceed to a definitive surgical treatment, note pre-operative radiation is allowed on study for patients with progressive disease preoperatively. It is encouraged to keep subjects on study and to evaluate surgical specimens as per planned biomarker and pathological assessments.

Patients who undergo surgical resection and have had good response as defined by necrosis on histopathological resection may continue for additional treatment post-operatively. If post op radiation is administered the subjects come off treatment (see [3.1.5 End of Treatment](#) for details) and will remain on study in Long Term Follow-up.

Safety Monitoring

The Study will use a safety-run-in to evaluate the PK and tolerability when at least 6 subjects have been enrolled and completed at least the planned Cycle 1. All available safety tolerability data will be presented and discussed at the SRC.

If after the evaluation by the SRC the study proceeds after evaluation of the initial subjects a second evaluation as defined in the statistical section. An evaluation of the totality of the data available to complete the planned 4 cycles and to review efficacy and histopathological response data and will provide the sponsor a recommendation as to proceed with expansion or to halt enrollment of the group.

Group 2: Comparison of the RP2D of SQP33 Administered Over 3 vs 5 Days

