Only patients who have had objective evidence of response or whom in the opinion of the multidisciplinary treatment team determined to have achieved a clinical benefit may defer surgery at this point, the study will allow up to 4 additional cycles pre-operatively, at which point all patients should undergo exploratory surgery and or extremity tumor resection.

If a patient had a response, they may receive up to 4 additional cycles post operatively but not to exceed 12 cycles within the study. Surgical markers will be used to indicate the tumor

bed for injection with SQ3370 or if suitable for the metastatic patients, a metastatic lesion may be injected.

Any patient at any point who has been determined to have progressive disease has reached the end of treatment and will proceed to a definitive surgical treatment, note pre-operative radiation is allowed on study for patients with progressive disease preoperatively. It is encouraged to keep patients on study and to evaluate surgical specimens as per planned biomarker and pathological assessments.

Patients who undergo surgical resection and have had good response as defined by necrosis on histopathological resection may continue for additional treatment post-operatively. If post op radiation is administered the patients come off treatment (see 3.1.5 End of Treatment for details) and will remain on study in Long Term Follow-up.

Safety Monitoring: The Study will use a safety-run-in to evaluate the PK and tolerability when at least 6 patients have been enrolled and completed at least the planned Cycle 1. All available safety tolerability data will be presented and discussed at the SRC. If after the evaluation by the SRC the study proceeds after evaluation of the initial patients a second evaluation as defined in the statistical section. An evaluation of the totality of the data available to complete the planned 4 cycles and to review efficacy and histopathological response data and will provide the sponsor a recommendation as to proceed with expansion or to halt enrollment of the group.

Group 2: Comparison of the RP2D of SQP33 Administered Over 3 vs 5 Days

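### SAP 11.7 does not exclude the effect of radiation given after progression from the Group 1 pathological response rate

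*SAP*

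**What the plan says.** Phase 2a SAP 11.7 describes a consultation after Cycle 4 with the surgeon and oncologist, possibly followed by more cycles. It then gives the scoring rule: "When the surgery does take place, a tumor section will be analyzed to determine if there is a pathological complete response or pathological partial response". Its summary measure follows: "The histopathologic response categories (CR+PR) will be summarized with the number and percentage of patients", with an exact two-sided 95% confidence interval. Protocol 8.4.2.2 lists the endpoint by name only.

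A Group 1 patient with progressive disease stops SQ3370 and goes to definitive surgery. Four places allow radiation before that surgery:
- Protocol synopsis, Group 1: "note pre-operative radiation is allowed for patients with progressive disease pre-operatively on study at this point".
- Protocol 3.1.4.1, where such radiation "is allowed for patients with PD pre-operatively on study at this point".
- Protocol 3.5.1: "note pre-operative radiation is allowed on study for patients with progressive disease preoperatively".
- Phase 2a SAP 2.3: "pre-operative radiation is allowed on study for patients with progressive disease preoperatively".

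The last three also address the specimens of these patients. In the SAP's words: "It is encouraged to keep patients on study and to evaluate surgical specimens as per planned biomarker and pathological assessments".

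Best overall response is treated differently. SAP 11.1 and Protocol 8.4.2.2 close it at the first of documented progression, death or subsequent therapy.

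**The concern.** Pre-operative radiation is offered to Group 1 patients whose disease has progressed on SQ3370. If their specimens are then scored under 11.7, a pathological response produced wholly or partly by radiation can be reported as a response to SQ3370. The error runs in the drug's favour, and a single-arm group has no control to reveal it.

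The documents themselves treat radiation as a separate tumour treatment. Protocol 3.1.5 lists starting radiotherapy among the reasons to end study treatment. Protocol 4.2.1.1 excludes earlier radiation to the affected limb, so any radiation effect in a limb specimen would arise after entry.

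At stake is the interpretation of a Group 1 secondary endpoint. Under Protocol 3.5.1 and SAP 2.3, the SRC reviews histopathological response with the other efficacy data before recommending that the group expand or halt.

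**Working it through.** **1. The plan's own figure.** The only stated Group 1 design figures concern RECIST objective response: at most 3/15 stops at Stage 1, at most 13/46 rejects the drug, with null 0.20 and target 0.35 (Protocol 8.3; SAP section 4). Exact binomial calculation:
- Probability of early termination = P(X ≤ 3 | n = 15, p = 0.20) = 0.6482 (stated 0.648).
- Expected sample size = 15 + (1 − 0.6482) × 31 = 25.91 (stated 25.91).
- P(X1 ≥ 4 and X1 + X2 ≥ 14) = 0.0498 at p = 0.20 and 0.7046 at p = 0.35 (stated 0.0498 and 70.5%).

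The figures reproduce. They do not depend on 11.7, because the counted response is closed at progression, before any of this radiation is given. The shorter ORR definition in SAP 8.6 also stops at progression. No target, sample size or power is stated for pathological response.

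**2. The rules side by side.**
- Radiographic response (SAP 11.1): closes at progression, death or subsequent therapy.
- Pathological response (SAP 11.7): scored at surgery, with no closing event.
- Progressors (Protocol 3.1.4.1 and 3.5.1; SAP 2.3): SQ3370 stops, radiation is allowed, surgery follows, and assessment of the specimen is encouraged.

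No section says that an irradiated specimen is left out or scored as a non-response.

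**3. Illustrative size.** All three inputs are assumptions, because the documents give none:
- share progressing before surgery, *a*: 20% to 40%
- share of those irradiated before surgery, *b*: 50% to 100%
- share of those scored pathological CR or PR, *c*: 10% to 30%

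Addition to the reported rate = *a* × *b* × *c*.
- Low: 0.20 × 0.50 × 0.10 = 0.01, or 1 percentage point; 46 × 0.01 ≈ 0.5 patients.
- High: 0.40 × 1.00 × 0.30 = 0.12, or 12 points; 46 × 0.12 ≈ 5.5 patients.

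This is a gross figure: it treats every response in an irradiated progressor as caused by radiation.

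**4. What a reader of the report would see.** Suppose 5 of 46 patients respond without intervening therapy and 4 irradiated progressors are also scored as responders.
- All counted: 9/46 = 19.6% (exact 95% CI 9.4% to 33.9%).
- Irradiated specimens not counted: 5/46 = 10.9% (3.6% to 23.6%).

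**The case against.** The strongest reply is that 11.7 concerns only patients on the planned path. Its scoring sentence follows directly on the post-Cycle 4 consultation, and the protocol merely encourages assessment of progressors' specimens without calling them responders. Part of this stands: the accurate statement is that radiation effect is not excluded, and a reader who infers that the plan positively counts irradiated specimens as SQ3370 responses goes too far. But the scoring sentence is not limited to patients who reach that consultation, and SAP 2.3 directs progressors' specimens to the same planned pathology.

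Other stronger readings are tempting but unsupported:
- *Stage decisions are distorted.* They are not; the Simon counts use objective response. The SRC also sees the totality of the data in an open-label trial, and nothing suggests that it would see a bare pathological rate without progression and radiation status.
- *Limb salvage after radiation is credited to SQ3370.* SAP 11.8 contains no crediting rule; it defers data collection and analysis to a later SAP version.
- *Unresected patients drop out of the denominator.* SAP section 11 uses the Treated/Full set, SAP 8.4 bases percentages by default on the defined population, and neither the Treated/Full nor the Efficacy Evaluable set requires resection. SAP section 9 names the Efficacy Evaluable set for response endpoints, which is a separate inconsistency.
- *The bias is very large.* Taking *c* = 70% at the upper end gives 0.40 × 1.00 × 0.70 = 28 points, but no document supports such inputs. Irradiation of every progressor is itself doubtful, since one entry route in Protocol 4.2.1.1 is for patients who decline radiation.
- *Every progressor should be a pathological failure.* RECIST progression includes new lesions anywhere (Protocol 6.18.2), Group 1 admits metastatic disease, and the drug is activated locally. An unirradiated patient with a new distant lesion may still have a real response in the injected tumour.

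It is also fair to say that 11.7 does not define pathological CR or PR. The necrosis wording in Protocol 3.5.1 governs post-operative continuation, not this endpoint. That gap needs filling too, but filling it would not settle how irradiated specimens count.

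**Conclusion.** The concern holds as a gap in the endpoint definition. Followed as written, SAP 11.7 can credit radiation effect in patients who failed SQ3370 to the Group 1 pathological response rate, because it lacks the intervening-therapy cut-off given to best overall response. This conclusion rests on the text alone.

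The size does not. The range of 1 to 12 percentage points depends wholly on the assumed rates of progression, irradiation and pathological response. The endpoint is secondary and carries no hypothesis test, so no stated error rate changes. The consequence is a possibly favourable bias in a descriptive rate that informs the SRC's recommendation.

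**What to change.** In SAP 11.7:
- State that a specimen resected after radiation or other non-protocol anticancer therapy, given between the first SQ3370 dose and surgery, does not count as a pathological response.
- Keep those patients in the Treated/Full denominator as non-responders, and say explicitly that treated patients who are not resected are handled the same way.
- List the irradiated specimens separately.
- Report pathological findings in unirradiated RECIST progressors separately or as a sensitivity analysis, not automatically as failures.

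When 11.8 is written, consider the same intervening-therapy rule for surgical outcome.

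Protocol 5.9.2 does not permit concomitant radiotherapy in Phase 2a, while the Group 1 text in the synopsis, 3.1.4.1, 3.5.1 and SAP 2.3 allows it after progression. These passages must be reconciled. The analysis rule above changes no patient's care.

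The cost is a few sentences. The Phase 2a SAP is marked version 0.1, so the rule can be set before Stage 1 data are seen; added later, it could look data-driven. Progression and subsequent-therapy dates are already needed for best overall response and time to first subsequent therapy. The downside is that the reported rate may be lower, and a genuine SQ3370 effect in an irradiated patient would appear only in the separate listing.
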